Vitrectomy surgery (PPV) involves 'keyhole' surgery to the eyeball, via three tiny (23/25 gauge) incisions to the sclera. This procedure is carried out in the operating room, under regional anaesthetic (a freezing injection to the retro-bulbar space, the space behind the eyeball, where nerves which sense pain and control eye movement are situated) plus sedation (medication to reduce patient anxiety). During PPV, the vitreous gel is removed from the eye using a fine metal instrument called a 'vitrector'. The vitreous gel is removed to allow space for a larger gas bubble than is possible in PnR, and also to relieve any vitreous traction which may otherwise impair reattachment of the retina. A large gas bubble (same gases as mentioned for PnR) is injected (to reattach the retina, as in PnR), and laser or cryotherapy is applied around the retinal tear to secure it (as in PnR). After treatment, a patient may be required to maintain a 'head posture' (for example, head tilt to left) for up to one week. The purpose of this 'head posture' is to support the area of the retinal tear optimally, by 'floating' the gas bubble up against it. As the gas bubble is larger in PPV, the head posturing requirements are less strict. The gas bubble reabsorbs after 2-6 weeks, depending on the gas selected. The surgery takes 1-1.5 hours. The success rate (i.e. the proportion of patients in whom the retina becomes attached after one treatment) is reported as being as high as 90% in the scientific literature.^{7,12,13}

Scleral buckling (SB) is another method used for repair of RD that involves encircling the eye with a silicone band, and may or may not involve the use of a gas bubble. This

has been reported to have better visual results than PPV in phakic patients.¹⁵

Another surgical technique for repair of RD is PPV combined with SB (PPV/SB), and this is used commonly in treatment of larger or more complex detachments. The surgery combines the two techniques, and involves the use of a large and often long-acting gas bubble similar to what is done in PPV surgeries.

All the treatment options may be associated with complications such as bleeding, infection, increased intraocular pressure or cataract. The risk of a sight threatening complication such as a severe intraocular infection or hemorrhage is less than 1:1000. The risk of cataract development (clouding of the lens, requiring cataract extraction surgery) is less in PnR^{11,14} and SB compared to PPV.¹⁵

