Distortion and retinal displacement after retinal detachment repair

Image distortions such as metamorphopsia and micropsia are common complaints after surgery for retinal detachment. In 2010 Shiragami et al were the first to demonstrate hyper-fluorescent lines, adjacent to the retinal blood vessels in Fundus auto-fluorescence imaging (FAF) of the retina after retinal detachment (RD) repair surgery.²⁶ They proposed a theory in which these lines which are called also Retinal Vessel Printing (RVP) correspond to the area where the retinal blood vessels were located before the retinal detachment. According to this theory the RVP in FAF imaging is due to increased metabolic activity of RPE cells. Prior to surgery these RPE cells were obscured to light rays by retinal blood vessels while after surgery, due to displacement of the retina, these RPE cells became exposed to the light which leads to increase in the cells metabolic activity. This increase in metabolism is thought to be the cause for the hyper fluorescence seen in FAF imaging. Displacement of the retina after RD repair surgery can serve as anatomy basis of vision distortion. Moreover, these reference lines allow us to quantify the displacement of the retina after retinal detachment surgeries. By doing this, we can compare retinal displacement of different retinal detachment repair surgeries and may reduce post operation visual distortion.

Since Shiragami's first report, several other studies looked into retinal displacement after RD repair²⁶⁻³², epiretinal membrane³³ and macular hole³⁴. Codenotti et al have shown that retinal displacement ratio is higher in patients with intravitreal gas compare to patients with silicon oil (71.4% vs. 22.2%).²⁷ Lee et al proposed a way of quantifying the rotational displacement of the retina.²⁸ They showed that there is more than a simple rotation and probably also a temporal stretch of the retina. Recently Dell'omo published the biggest study so far of 125 patients after pars plana vitrectomy (PPV) with 35.2% of patient showed signs of retinal displacement.³⁰

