- Inability to sign on informed consent.
- Patient is unwilling or unable to follow or comply with all study related procedures or to sign informed consent form

Criteria for participant withdrawal from study: - Patient withdraws consent

(v) Interventions

The only interventions in the study are performed at the 3 and 12 month postoperative visit, and include fundus imaging (FAF and OCT), and sensory testing with the M chart and the Aniseikonia test, as detailed below.

Participants will be chosen from those undergoing either scleral buckling alone or scleral buckling combined with vitrectomy for repair of a macula-off retinal detachment. Patients are not randomized to the procedure, rather the procedure is chosen by the surgeon in the best interests of the patient.

In the event of primary intervention failure (i.e. failure of retinal re-attachment following primary intervention), the decision to proceed with secondary intervention, and the nature of such intervention, will rest with the treating physician in conjunction with the patient. Secondary intervention may involve any surgical procedure, as deemed clinically appropriate.

Note: Additional laser retinopexy, cryotherapy, gas injection or head positioning are not considered a failure.

(vi) Timing of observationsSee flow diagram (Appendix 1)

Imaging

Fundus AutoFluorescence (FAF)

Fundus autofluorescence (FAF) imaging is a noninvasive imaging method and requires relatively little time. It highlights the fluorophores accumulating in lipofuscin (LF) within retinal pigment epithelium cells (RPE). No radiation is involved therefore this imaging method is safe without any clear contraindications.

M Chart

Recently, several tools have been developed for quantification of metamorphopsia severity including M-CHARTS (Inami Co., Tokyo, Japan). In the patients with metamorphopsia, a straight line appeared curved or irregular. On M-CHARTS, straight lines are replaced with dotted lines, and the dot intervals (range: 0.2° - 2.0°) are changed from fine to coarse. With increasing dot interval, the line distortion decreases until the dotted line becomes straight. The visual angle that denoted the dot interval of the line seen as straight was considered as the patient's M-CHARTS score. When a

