The following clinical data will be obtained from each patient: age, gender, extent of the detachment (quadrants), duration of subjective symptoms (days), vitreous status (presence/absence of vitreous hemorrhage), macular status (attached/on or detached/off), the location of main retinal tears (fundus sketch), refractive power (emmetropic, hyperopic, myopic <6 or > 6 diopters, lens status (phakic or pseudophakic) and medications in use.

(x) Sample size

Sample sizes were calculated to appropriately power the study. A total sample size of 40 subjects with macula-off detachments undergoing scleral buckles will be recruited. A second group of 40 subjects with macula-off retinal detachments undergoing combined vitrectomy and scleral buckle placement will also be recruited. Anticipating a dropout rate of 20%, we calculated a total of 100 patients in the entire study.

IV. Data management

Initial data collection (clinical examination findings, visual acuity, and questionnaire data) will take place in a paper format. Subsequently, this data will be transferred to a digital database (Microsoft Excel). Paper data will be stored in a locked filing cabinet in the principal investigator's office and away from the study data, and will be destroyed once digital data entry has taken place. The digital spreadsheet will be held on a password protected computer in a locked room, and an encrypted memory stick.^[1] At recruitment, each patient's name and date of birth will be obtained to facilitate onward administration of follow-up appointments and safety monitoring and stored on a face sheet (master linking log). The face sheets will be stored in a locked filing cabinet, away from the study data. Each patient will be allocated a unique study identification number, which will be used to label all paper and digital data pertaining to that patient. The face sheets (master linking log) and all paper/electronic data will be destroyed once publication takes place. The de-identified study data will be destroyed five years after publication has taken place.

V. Consent:

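### Does the lack of a listed tamponade item prevent the study from answering its question about SB versus PPV+SB?

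*Protocol*

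**What the plan says.** Section I (Background, interventions) says that SB "may or may not involve the use of a gas bubble", and that the combined operation "involves the use of a large and often long-acting gas bubble similar to what is done in PPV surgeries". The Background on displacement reports from a cited study that the "retinal displacement ratio is higher in patients with intravitreal gas compare to patients with silicon oil (71.4% vs. 22.2" per cent).

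Section III(v) leaves the choice of operation to the surgeon, without randomisation, and adds: "Note: Additional laser retinopexy, cryotherapy, gas injection or head positioning are not considered a failure".

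The list of patient data is under Assessment of Clinical Parameters, within III(ix) Screening Procedures. It opens with "The following clinical data will be obtained from each patient" and begins with "age, gender, extent of the detachment (quadrants), duration of subjective symptoms (days), vitreous status (presence/absence of vitreous hemorrhage". It goes on to macular status, tear location, refraction, lens status and medications. It has no item for tamponade.

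Section IV states: "Initial data collection (clinical examination findings, visual acuity, and questionnaire data) will take place in a paper format". It also states: "The face sheets (master linking log) and all paper/electronic data will be destroyed once publication takes place".

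The aim (section II) is to compare displacement and distortion after SB with that after PPV+SB. The primary outcome, in III(vii), is the presence of retinal vessel printing on autofluorescence imaging. Section VI plans a chi-squared test for categorical data.

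**The concern.** By the protocol's own account, gas use is expected to differ between the groups, and the type of tamponade is associated with the primary outcome. The hypothesis in III(i) is worded causally, and the surgeon chooses the operation, so recorded covariates are the main help in interpreting a difference. Later gas injections do not count as failures, so those eyes would stay in the analysis unmarked.

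If tamponade were never recorded, the report could not give the share of SB eyes that received gas, and it could not explore whether gas or vitrectomy lay behind a difference. An analysis plan cannot use a variable that nobody collected, and once the linking log is destroyed the information could not be recovered.

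**Working it through.** **1. Is the list meant to be the whole dataset?** Three texts bear on this.

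- The list in III(ix) belongs to screening and holds pre-operative items. It does not name the operation performed, which is the grouping variable, nor reattachment, nor secondary surgery. The study cannot be run without the first of these, so the list is not complete.
- The parenthesis in section IV describes what starts on paper. It names neither autofluorescence nor OCT imaging. Read as a full inventory, it would mean that the primary outcome is not collected.
- The flowchart in Appendix 1 survives only as fragments. It shows 12 months and not the 3-month visit of III(v), so an item missing there proves little.

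It is true that no text names tamponade. That does not establish that tamponade goes unrecorded.

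**2. Could it be recovered?** Section IV destroys the linking log at publication. Until then, through recruitment, follow-up and analysis, each study number can be matched to the operative note. That the note records tamponade is an assumption, but an ordinary one for this surgery.

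**3. What does gas use do to the primary comparison?** Assume that gas eyes have the same displacement rate in both groups, that all PPV+SB eyes get gas, and that a share g of SB eyes does. Then

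SB rate = g × (gas rate) + (1 − g) × (no-gas rate).

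The table gives the exact power of the two-sided 5% Pearson chi-squared test with 40 eyes per group, the group size in III(x).

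| g | Case A: SB rate vs 35.2% | Power | Case B: SB rate vs 71.4% | Power |
|---|---|---|---|---|
| 0 | 8.0% | 88% | 22.2% | 99.7% |
| 0.10 | 10.7% | 77% | 27.1% | 99% |
| 0.25 | 14.8% | 57% | 34.5% | 93% |
| 0.50 | 21.6% | 27% | 46.8% | 63% |

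For example, Case A at g = 0.25 gives 0.25 × 35.2 + 0.75 × 8 = 14.8%.

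The 8% no-gas rate is assumed. In Case B the oil figure of 22.2% stands in for no gas. The 35.2% is the protocol's figure after vitrectomy, used here as a gas-eye rate.

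The fall down each column comes from gas being used in SB eyes. Writing gas use down alters none of these values, because the primary comparison stays as operated. The table therefore does not measure a cost of the missing field.

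**4. What would the field add?** Take Case A with g = 0.25.

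- Expected eyes with vessel printing: 40 × 0.148 = 5.9 in SB and 40 × 0.352 = 14.1 in PPV+SB.
- The same totals arise if gas is irrelevant and every SB eye has a 14.8% risk.
- The field would separate the two explanations only through the 10 SB gas eyes: 10 × 0.352 = 3.5 expected if gas drives displacement, 10 × 0.148 = 1.5 if it does not.

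Precision of SB with gas against PPV+SB, both at 35.2%, by the Newcombe–Wilson method:

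- Wilson limits for n = 10: 13.8% to 64.8%.
- Wilson limits for n = 40: 22.3% to 50.7%.
- Lower limit: −√[(35.2 − 13.8)² + (50.7 − 35.2)²] ≈ −26 points.
- Upper limit: +√[(64.8 − 35.2)² + (35.2 − 22.3)²] ≈ +32 points.

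The interval spans almost any plausible effect.

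**The case for a change.** The strongest case for a change is that the protocol supplies the reasons itself. Gas use differs between the operations by its own description, tamponade type is tied to the outcome by its own citation, allocation is not randomised, and a single field taken from the operative note costs almost nothing. If SB eyes often receive gas, readers would want to know how often.

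Part of this stands. Naming tamponade at primary surgery and any later gas injection would be a cheap descriptive improvement, and it would let the report state the share of SB eyes given gas.

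The rest does not carry a change. The cited contrast is gas against oil, and the title in the reference list places it after vitrectomy, so it does not size an effect of gas against no gas in buckled eyes. The aim compares operations as performed, and gas is described as part of the combined one. Separating vitrectomy from gas is a further mechanistic question that the aim does not pose. Nor would the field settle that question. Gas within SB is given by clinical choice, so the contrast is open to confounding by indication. If no SB eye receives gas, vitrectomy and gas stay inseparable however carefully gas is recorded.

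**Conclusion.** No change to the plan is needed. The protocol does not list tamponade, but the list in question is a screening list that also omits the operation itself, so it is not evidence that the information is lost. Followed as written, the plan still answers its stated aim, and the primary comparison is the same whether or not the field exists. What is at stake is a descriptive line and an exploratory contrast, whose 95% interval would run from about −26 to +32 points with 10 SB gas eyes.

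This rests on two assumptions: that operative notes record tamponade, and that the investigators draw on them before the linking log is destroyed. The share of SB eyes given gas, and any effect of gas against no gas, are not in the protocol. The 10 eyes are an illustration, at a quarter of the SB group.

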STUDY PROTOCOL (Version 1, 1/17/2018)^[L1]_[SEP]

Title: Retinal displacement after scleral buckling (SB) versus scleral buckle combined with vitrectomy (PPV+SB) for the management of primary retinal detachment: ALIGN SB vs. PPV-SB. An extension of the study of “Retinal displacement after pneumatic retinopexy (PnR) versus vitrectomy (PPV) for the management of primary retinal detachment (ALIGN) NCT04089033.”

Principal Investigators:

[name]^[L1]_[SEP]

[name]

Co-investigators:

[name]^[L1]_[SEP]

[name]

[name]

[name]

[name]

[name]

[name]

[name]

Study coordinator:

Setting:

[figure not shown]
I. Background

Retinal detachment^[L1]_[SEP]

Rhegmatogenous retinal detachment (RRD) is an acute, sight threatening condition,

with an incidence of approximately 10 per 100,000 people.¹ During normal ageing, the transparent vitreous gel (see figure 1:A), which fills the eye, liquefies and shrinks, and eventually detaches in 80% of the eyes. When detachment of the gel occurs, a tear in the retina may form (see figure 1:B). Liquified gel may now enter under the retina via the retinal tear (see figure 1:C), resulting in detachment of the retina (see figure 1:D). Once retinal detachment occurs, sight loss usually develops within several hours to days.

Figure 1: Retinal detachment

Factors that predispose an individual to developing retinal detachment are myopia (near sightedness), advancing age, trauma, and certain hereditary conditions.² Without any surgical intervention by a vitreoretinal surgeon, retinal detachment almost invariably results in permanent sight loss in the affected eye. There is an increased risk of delayed visual rehabilitation the longer the wait for surgery is.³ Interventions for rhegmatogenous retinal detachment may include Scleral Buckling (SB), Pneumatic retinopexy (PnR), Pars Plana Vitrectomy (PPV), and PPV+SB in which the primary objectives are to close and seal the retinal break and reattach the neurosensory retina to the RPE.⁴⁻¹⁰ The choice of which procedure to perform depends on the clinical examination and the surgeon's discretion as to which will be best for the patient in that specific scenario.

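### The baseline list has no defined measure of detachment complexity, a factor the protocol itself ties to PPV+SB, so adjusting for every listed item could leave residual confounding by indication.

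*Protocol*

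**What the plan says.** **Allocation.** Protocol III(v) states: "Patients are not randomized to the procedure, rather the procedure is chosen by the surgeon in the best interests of the patient". The background section on retinal detachment agrees: "The choice of which procedure to perform depends on the clinical examination and the surgeon's discretion".

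**What drives the choice.** The background section on interventions says of PPV combined with SB that "this is used commonly in treatment of larger or more complex detachments". This names two selection factors, size and complexity.

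**What is recorded.** In III(ix), Assessment of Clinical Parameters, the list opens with "The following clinical data will be obtained from each patient". It includes "extent of the detachment (quadrants), duration of subjective symptoms (days), vitreous status (presence/absence of vitreous hemorrhage", then macular status, "the location of main retinal tears (fundus sketch", refractive category, and "lens status (phakic or pseudophakic) and medications in use". Age and gender are also listed.

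**The wait for surgery.** The background says: "There is an increased risk of delayed visual rehabilitation the longer the wait for surgery is". Visual acuity at 12 months is a secondary outcome in III(vii). The primary outcome is retinal displacement, judged by vessel printing on autofluorescence imaging.

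**Analysis.** Section VI gives t-tests, non-parametric tests and a chi-squared test at 0.05. It names no covariate adjustment.

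**The concern.** In a cohort where the surgeon assigns the procedure, the comparison can be no better than the measurement of the factors behind that choice. The protocol names two such factors. One, size, has a field. The other, complexity, has neither a field nor a definition. Vitreous haemorrhage, location of the main tears and lens status describe parts of a case, but the protocol does not present them as a measure of complexity.

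If complex eyes go more often to PPV+SB and also displace more, SB will look better for reasons unrelated to the operation. That is the direction of the study hypothesis. A result favouring SB could then not be separated from SB having been given to simpler eyes.

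This is a data-collection point and is distinct from the choice of test. A statistical analysis plan that is not shown here may add covariates, but only from data that were collected.

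**Working it through.** **1. The plan's own figure.** III(x) has 40 + 40 = 80 evaluable eyes and 20% dropout: 80 / (1 − 0.20) = 100, which matches the stated total. The point does not turn on this figure; it only fixes 40 per group for the illustration below.

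**2. Named selection factors against the list in III(ix).**

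| Factor named in the background | Field in III(ix) |
|---|---|
| Larger detachment | Extent in quadrants |
| More complex detachment | None defined; partial descriptors are vitreous haemorrhage, location of main tears and lens status |
| Longer wait for surgery (linked to visual rehabilitation only) | Symptom duration in days, end point not stated |

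**3. How large the bias could be.** All inputs in this step are assumed. Complexity is a yes/no factor, the procedure has no true effect, and nothing is adjusted for.

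Rate in a group = (share complex × risk in complex eyes) + (share simple × risk in simple eyes).

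Spurious difference = (difference in share complex) × (difference in risk).

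| Case | Share complex, PPV+SB v SB | Risk, complex v simple | PPV+SB rate | SB rate | Spurious difference |
|---|---|---|---|---|---|
| Mild | 40% v 20% | 45% v 35% | 0.4×0.45 + 0.6×0.35 = 0.39 | 0.2×0.45 + 0.8×0.35 = 0.37 | 0.20×0.10 = 0.02 |
| Middle | 50% v 20% | 50% v 30% | 0.5×0.50 + 0.5×0.30 = 0.40 | 0.2×0.50 + 0.8×0.30 = 0.34 | 0.30×0.20 = 0.06 |
| Strong | 60% v 10% | 60% v 30% | 0.6×0.60 + 0.4×0.30 = 0.48 | 0.1×0.60 + 0.9×0.30 = 0.33 | 0.50×0.30 = 0.15 |

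The false-positive rate is the chance that an uncorrected two-sided chi-squared test at 0.05 rejects with 40 v 40 at these rates. Exact binomial enumeration gives 5.5%, 8.6% and 28.5%. The protocol does not state sidedness; two-sided is assumed.

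**4. A second set of assumptions.** Here the PPV+SB rate is anchored at 35.2%, the displacement rate the background quotes from a series of PPV patients. Let q1 and q0 be the shares complex in PPV+SB and SB, and RR the risk ratio for complexity.

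Base risk = 0.352 / (1 + q1(RR − 1)); SB rate = base × (1 + q0(RR − 1)).

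- q0 = 0.2, q1 = 0.3, RR = 1.5: base = 0.352/1.15 = 0.306; SB rate = 0.306×1.1 = 0.337; difference 1.5 points; false-positive rate 5.2% (normal approximation).
- q0 = 0.2, q1 = 0.5, RR = 3: base = 0.352/2 = 0.176; SB rate = 0.176×1.4 = 0.246; difference 10.6 points; 17.6%.
- q0 = 0.1, q1 = 0.5, RR = 3: SB rate = 0.176×1.2 = 0.211; difference 14.1 points; 28.6%.

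**5. What these figures do not show.** Both sets give bias before any adjustment. Adjusting for extent and the partial descriptors would remove some of it, by an amount the documents do not allow anyone to compute.

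**6. Room for covariates.** If displacement is near 35.2% in 80 eyes, 80 × 0.352 ≈ 28 events are expected. That supports only a few covariates.

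**The case against.** **The list is not silent on complexity.** Several items describe the case, and eligibility narrows the mix: primary, macula-off detachments only, with earlier detachment, earlier vitreoretinal surgery and other structural retinal disease excluded. This stands, and for that reason the point is the lack of a defined measure. It does not remove the point, because no criterion excludes a complex primary detachment. The protocol does not define complexity, so break number, break size and proliferative grade are offered only as examples.

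**The figures are assumed and unadjusted.** This also stands. The mild case is barely above the nominal 5%. The figures show a possible range and do not estimate residual bias.

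**Records could be searched later.** Fundoscopy is done at every visit, so some information may exist in clinical notes. But section IV has paper data destroyed after entry and the linking log destroyed at publication, and nothing requires notes to describe complexity in a uniform way. Later recovery is possible but uncertain.

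**More covariates would overload the model.** With about 28 events this is a fair warning. It limits the form of the fix and is no reason to leave the factor unrecorded.

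**A stronger reading on the wait.** A reader might infer that the wait for surgery is also unrecorded and confounds the comparison. The documents do not support that. Symptom duration is a partial measure of delay, and a full one if counted to the operation. The date of surgery must be known to time the 3 and 12 month postoperative visits. The background ties the wait only to delayed visual rehabilitation. It does not tie it to the choice between SB and PPV+SB or to displacement, and nothing shows that the wait differs between groups.

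**Conclusion.** The point holds for complexity. The protocol names it as a reason for PPV+SB, leaves the choice to the surgeon, and collects no defined measure of it. Adjusting for every listed item could leave residual confounding by indication, favouring SB if complex eyes displace more. A reader might go further and conclude that imbalance is certain or that the result must be biased. The text says only that PPV+SB is commonly used for such eyes, and gives no figures on complexity and displacement, so that conclusion is not supported.

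The size is unknown. Under the assumed inputs and before adjustment it runs from 2 to 15 percentage points, with a false-positive rate of about 5.5% to 28.5%. The range extends from negligible to serious, and without the field nobody could tell which applies.

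On the wait, only a clarification is warranted: symptom duration has no stated end point, which matters for reading 12-month acuity.

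**What to change.** **Main change, III(ix).** Add to the baseline form a prespecified complexity descriptor, read at the pre-operative fundoscopy already done. Number of breaks, size of the largest break and grade of proliferative change are examples; the investigators should settle the definition before data are examined. Report its balance between groups. Include it with extent in an adjusted SB versus PPV+SB comparison, using one summary complexity variable or a propensity score, because about 80 eyes support only a few covariates.

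**Secondary clarification.** Keep symptom duration, state whether it runs to presentation or to surgery, and record the date of surgery so that the interval is available for the 12-month acuity comparison.

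**Cost.** A few form fields and a short amendment, with no added visit, procedure or patient and no change to clinical care. The downside is slightly less precision from the added covariate. Confounding by factors that remain unrecorded would still be possible and should be stated as a limitation.

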patient was tested with vertical dotted lines, the result was defined as the vertical M-CHARTS score. After the M-CHARTS were rotated 90°, the horizontal M-CHARTS score also was measured according to horizontal dotted lines³⁵.

Aniseikonia test

Aniseikonia is a phenomenon in which the size or shape of perceived images differs between eyes. The anomaly is reported to be associated with interocular differences in refractive error and some retinal diseases. Following successful repair for rhegmatogenous retinal detachment, some patients have complained that objects appeared distorted in size or shape. The Aniseikonia Test measures the ratio of image size difference between the 2 eyes³⁶.

(vii) Outcome measures^[11]_[SEP]

Primary outcome:

- retinal displacement by the presence of retinal vessels printing on FAF imaging.

Secondary outcome:

- Visual Distortion measured with M chart.
- Anisokenia testing.
- Optical Coherence Tomography (OCT) changes.
- Metamorphopsia according to the patient symptoms.
- Visual acuity (ETDRS 12 months post intervention)

- Metamorphopsia questionnaire^[12]_[SEP]

(viii) Recruitment plan

Recruitment will begin after Research Ethics Board approval has been granted and will continue until the required number of patients are enrolled and have completed the study. Patients visiting the retina clinic with primary RRD will be given the option to participate if they meet the criteria. Based on our clinic's routine volume, we anticipate recruiting approximately 4 patients per sub-study per week, with complete recruitment over a 12-month period. Each patient will be followed for 12 months.

(ix) Screening Procedures

Retinal Displacement after scleral buckle vs pars plana vitrectomy with scleral buckle for primary rhegmatogenous retinal detachment – Protocol # 18-085, version 1, 1/17/2018

Patients will be screened by the investigators in the same manner as standard patients. The tests to be performed are typically used for diagnosis and follow-up of retinal detachment: best-corrected Snellen visual acuity assessment, slit-lamp exam, tonometry, fundoscopy, and Optical Coherence Tomography (OCT) at every visit. ETDRS visual acuity (ETDRS - 'Early treatment of Diabetic Retinopathy Study' – this study defined a method of visual acuity assessment that has become the gold standard for use in eye research) will be assessed at 12 months after the treatment for RRD.

Assessment of Clinical Parameters:

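### Does the sample-size section give two different enrolment numbers, 80 and 100, and leave the plan without a usable target?

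*Protocol*

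**What the plan says.** Protocol III(x), Sample size, opens with the claim "Sample sizes were calculated to appropriately power the study". It then gives the first group, "A total sample size of 40 subjects with macula-off detachments undergoing scleral buckles will be recruited", and says that a second group of 40 "undergoing combined vitrectomy and scleral buckle placement will also be recruited". It closes with "Anticipating a dropout rate of 20%, we calculated a total of 100 patients in the entire study". Section V, Consent, repeats the 20% dropout figure and attributes it to patients who live far from the sites.

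III(viii), Recruitment plan, says that recruitment "will continue until the required number of patients are enrolled and have completed the study", that "we anticipate recruiting approximately 4 patients per sub-study per week, with complete recruitment over a 12-month period", and that "Each patient will be followed for 12 months".

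The primary outcome in III(vii) is binary: "retinal displacement by the presence of retinal vessels printing on FAF imaging". Section VI assigns a chi-squared test to categorical data, a 0.05 significance level and a per-protocol analysis. No expected displacement rate for either procedure, no target difference and no power is stated.

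**The concern.** Three things catch the eye.

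- **Enrolment number.** The same 40 per group appears as the number recruited and as the number that the dropout allowance is meant to protect. It cannot be both. III(viii) then ends recruitment at a required number without saying whether that is 80 or 100. If a site stopped at 40 per group, the dropout allowance would go unused. Because the analysis is per protocol, the completers carry the result.
- **Recruitment plan.** The weekly rate and the 12-month period do not produce 100. Recruiting until patients have finished also cannot end within 12 months when each patient is followed for 12 months.
- **Basis for 40.** The text asserts a power calculation but omits the two rates and the power. A reader can neither check 40 nor judge how much a shortfall would cost.

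**Working it through.** **1. The plan's own figure.** Inputs: 40 and 40 from III(x); 20% dropout from III(x) and V.

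- Sum of the groups: 40 + 40 = 80.
- Inflation for dropout: 80/(1 − 0.20) = 100, or 40/0.80 = 50 per group. This matches the stated total exactly. The common mistake, 80 × 1.20 = 96, does not.
- Back-check: 100 × 0.80 = 80 completing, 40 per group.

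So 80 and 100 fit together as completing and enrolled.

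**2. The literal alternative.** If 80 were the number enrolled, 80 × 0.80 = 64 would complete, 32 per group. The figure of 100 would then have no purpose.

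**3. What the alternative would cost.** The protocol gives no rates, so this is an illustration only. Assume 50% v 20%, a two-sided 5% level (sidedness is not stated) and equal groups. With the pooled-variance formula, the mean rate is 0.35 and the two standard-deviation terms are √(2 × 0.35 × 0.65) = 0.6745 and √(0.50 × 0.50 + 0.20 × 0.80) = 0.6403.

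- n per group for 80% power = (1.96 × 0.6745 + 0.8416 × 0.6403)² / 0.30² = 38.5.
- Power at 40: Φ[(0.30 × √40 − 1.96 × 0.6745)/0.6403] = Φ(0.898) = 0.816.
- Power at 32: Φ[(0.30 × √32 − 1.96 × 0.6745)/0.6403] = Φ(0.586) = 0.721.

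Across assumed higher rates of 30% to 80%, the smallest difference with 80% power is 24 to 31 percentage points at 40 per group and 26 to 34 at 32. The background section's 35.2% (vitrectomy) and 71.4% (intravitreal gas) are not design inputs for this comparison. Used only as possible higher rates, they give detectable lower rates of about 9% and 41% at 40 per group. A sample of 40 per group is therefore compatible with a conventional calculation for a large difference. It is unverified, but it is not contradicted.

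**4. Recruitment.** Inputs from III(viii): about 4 a week per sub-study, 12 months of recruitment, 12 months of follow-up.

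- Time to 100 at 4 a week: 100/4 = 25 weeks. If each surgical group counts as a sub-study: 100/8 = 12.5 weeks.
- Yield of 4 a week over a year: 4 × 52 = 208.
- Rate needed to spread 100 over a year: 100/52 = 1.9 a week.
- Taken literally, recruiting until patients have completed would run at least 25 + 52 = 77 weeks, about 18 months. It would also make a dropout allowance unnecessary.

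The mismatch in rate is about twofold. It leaves slack in the forecast and does not put 100 out of reach. The stopping phrase conflicts with the 12-month period only if it is read as governing enrolment. Read as describing how long the study stays open, it agrees with the separate statements on recruitment and follow-up.

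**The case for a change.** The best argument for a change is practical. Sites in Minnesota and India must apply the same text, 50 per group is never written down, and surgeons choose the procedure, so group sizes are not controlled by randomisation. Under a per-protocol analysis, a group closed at 40 would be analysed at about 32. A protocol that claims a power calculation would also normally state its rates and power, and correcting the words would cost nothing.

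Part of this stands. The verb is wrong for the 40s, the inputs are absent, and the phrase that joins enrolment to completion is loose. The harm, however, requires a site to act on two sentences and ignore the next one in the same short paragraph, which names the dropout and the total for the whole study. The required number in III(viii) is most naturally that total. The missing inputs are a matter of reporting and may stand in an analysis plan that is not at hand; supplying them would not alter how many patients are enrolled. The weekly rate is offered as an approximate expectation from clinic volume, in units of a sub-study that the text does not define. Nor would a rewrite giving only a total of 100 improve matters. In a non-randomised cohort, enrolment could then stop at, say, 65 and 35, leaving 35 × 0.80 = 28 completing in the smaller group. The present text at least keeps 40 in view for each group.

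**Conclusion.** No change to the plan is called for. III(x) holds a clerical slip: the 40 per group is the number expected to complete, and the enrolment figure is 100, or 50 per group by the plan's own 20%. The arithmetic is exact, and analysts and sites can read it only one way once the paragraph is taken whole. The fall to 32 per group, and the drop from about 82% to 72% power, arise only on a reading that the next sentence rules out, and the power figures further assume 50% v 20%.

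The missing rates and power leave 40 unverified, not wrong; they belong in the report of the sample-size basis. The recruitment rate and period differ by about a factor of two in the harmless direction, and no estimate or test uses them. This conclusion rests on 100 being the working enrolment target and on the groups filling roughly equally, as the two 40s imply.
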